9.2.4. Study visits

It is planned to observe each subject for one cycle of treatment with Polyoxidonium. In accordance with the Summary of Product Characteristics (SmPC), the treatment course consists of 5-10 injections depending on the disease. Thus, study duration for individual subject will take 7-23 days. There will be 5-10 study visits coinciding with routine visits to receive Polyoxidonium injections at the health care centre (see Study flow chart in Table 1). If any visit (scheduled or unscheduled) occurs within 30 days after the last injection of Polyoxidonium as a part of routine practice, information on adverse events will be recorded.

Table 1. Study flow chart

Study procedures	Study visits			
	First injection	Interim visits (3 to 8, depending on indication)	Last injection	Follow-up*
Day	Day 1		Day 7 to 23	
Inclusion/exclusion criteria	X			
Informed consent	X			
Demographic data	X			
Height and weight	X			
Medical history	X			
Physical examination**	X	X	X	
Information about relevant infection, allergic condition, etc.	X	X	X	
Vital signs (blood pressure, heart rate, body temperature)**	X	X	X	
Laboratory tests**	X	X	X	
ECG**	X	X	X	
Other diagnostic procedures**	X	X	X	
Polyoxidonium administration	X	X	X	
Concomitant medications	X	X	X	
Adverse events	X	X	X	X
Investigator's and subject's assessment of tolerability and improvement			X	

*any visit (scheduled or unscheduled) which occurs within 30 days after the last injection of Polyoxidonium as a part of routine clinical practice

**if undertaken as a part of routine clinical practice. Results of laboratory tests, ECG examinations and other diagnostic procedures should be recorded only if performed within 3 days before subject's enrolment and (or) during the study period.

9.2.5. Study procedures

At the first visit, an investigator will inform a subject about the study (refer to Section 10.2.). If the subject consents to take part in the study and signs the written informed consent form, correspondent entry will be recorded in subject's medical records.

Then, a subject will be assigned a unique identification code, consisting of 4 symbols:

- number of the centre (2 digits),
- number of the subject in the center, by chronological order of selection (2 digits).

The investigator will maintain a subjects' identification list as part of the study file.

Actual assessments undertaken at each visit will be determined by clinical practice (see Study flow chart in Table 1). Subjects will not be administered any investigational medicinal products and/or medical procedures neither undergo any laboratory evaluations, diagnostic or monitoring procedures specifically for the purposes of this study.

Concomitant therapies will be administered at discretion of the investigator in accordance to routine clinical practice. According to the SmPC, Polyoxidonium may be administered as monotherapy or concomitantly with antibiotics, antivirals, antifungals, and antihistamines, bronchiolytics, corticosteroids, beta agonists, and cytostatic agents.

At the last visit (i.e., last injection visit), investigators and subjects will rate the overall tolerance of Polyoxidonium treatment as well as improvement.

9.2.6. Dosage and method of administration of Polyoxidonium

Subjects will be treated with Polyoxidonium in accordance with the posology and method of administration as per current version of SmPC approved by State Institute for Drug Control of Slovakia. Depending on the disease, Polyoxidonium treatment regimen consists of 5-10 injections:

- Acute inflammatory diseases, complicated forms of allergic diseases: 6 mg daily for 3 days, then on alternate days, 5-10 injections totally.
- Chronic inflammatory diseases: five 6 mg injections every other day, then twice weekly, 10 injections totally.
- Urogenital inflammatory diseases: 6 mg every other day, 10 injections totally.
- Chronic recurrent herpes simplex: 6 mg every other day, 10 injections totally.
- Allergic diseases: 6 mg daily for 2 days, then on alternate days, 5 injections totally.

Polyoxidonium is given intramuscularly as a slow injection (15-20 sec) into the deltoid muscle of the upper limb or outer upper quadrant of the thigh.

9.3. Variables

Where assessments are undertaken as a part of routine clinical practice, the following data will be recorded into eCRF:

- demographic data (year of birth, gender),
- height, weight,
- vital signs (blood pressure, heart rate, and body temperature),

- therapeutic indication specific information (e.g., details on infections (type, primary treatment administered and duration, hospitalizations), allergic disease, etc.).
- reasons for prescribing Polyoxidonium therapy,
- current concomitant diseases or those which occurred within 5 years before this study,
- concomitant medications,
- abnormal findings at physical examination,
- results laboratory tests (blood chemistry, haematology, and urinalysis),
- ECG abnormalities,
- information about other diagnostic procedures, if any;
- Polyoxidonium injections (dates and doses),
- Polyoxidonium discontinuation and reasons of discontinuation,
- adverse events,
- subject’s and investigator’s assessment of clinical improvement and Polyoxidonium tolerability.

A full medical history will be obtained by the investigator or qualified designee. The investigator or qualified designee will record on the eCRF prior medication taken by the subject within 30 days or longer as appropriate prior to Visit 1. The identity of the therapy, the dose, route of administration, and regimen, the dates started and stopped (or notation of “continuing” if that is the case), and the reason for use must be recorded. The concomitant medications will be documented in the same manner all over the subject’s participation in the study.

Results of laboratory tests, ECG examinations and other diagnostic procedures should be recorded only if performed within 3 days before subject’s enrolment and (or) during the study period.

9.3.1. Definition of event of interest

In case of suspected adverse renal effect investigator will be encouraged to apply clinical judgement, to perform diagnostic workup and collect as much data as possible to confirm or reject the diagnosis of renal impairment. The signs and symptoms of renal toxicity, indicative of potential renal impairment include but are not limited to: increased blood concentrations of creatinine, potassium, blood urea nitrogen, urine protein levels, ECG changes, characteristic to elevated potassium levels; symptoms of intoxication, e.g. fatigue, nausea, vomiting.

These data for each subject for whom adverse renal effect is suspected will be reviewed and adjudicated by an independent assessor. This final adjudicated conclusion will be qualified as event of interest (a case of adverse renal effect) or suspicion about renal toxicity will be rejected.

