9.9. Limitations of the research methods

Due to limited data concerning the signal of outcome of interest no test hypothesis for this study has been formulated.

The limitations of this study are characteristic to other studies of a similar design (i.e., real life observational studies). Information concerning the potential confounders will be difficult to control.

Because of non-randomized design, absence of blinding and control group selection bias and information bias may occur. To mitigate this risk and ensure that study population represents the source population, investigators and study sites will be selected randomly from the available list of Slovakian immunologists and allergologists. The investigators will be trained and encouraged to enroll all eligible patients consecutively and keep screening logs to document the number of patients invited (refer to Section 9.2).

Some misclassification of outcome variables as well as confounders is possible. A validation is planned which will assess the rate of misclassification and correct the estimates accordingly. To mitigate the risk of information bias, investigators encouraged to collect as much data concerning the event of interest (adverse renal effects) as possible within the frame of routine practice. A set of available clinical data about the event of interest, presented in a standard format, will be adjudicated by an independent assessor.

Misclassification of exposure is not expected to happen. However due to nature of dosing regimen study population may be not homogenous in terms of duration of treatment and dosing schedule.

Since inclusion and exclusion criteria are very limited, it is expected that enrolled subjects will represent the source population (i.e., target patients of Polyoxidonium therapy) in Slovakia. To document the number of patients invited and assess selection bias in subject recruitment, screening logs will be used.

Subjects included in the study are expected to be representative of the source population (i.e., patients for whom Polyoxidonium is routinely prescribed in Slovakia) in terms of gender, age distribution, socio-economic class, indication, concomitant diseases.

Confounding by known and unknown covariates may happen:

- Patients with variety of diseases and medical conditions are planned to enroll in scope with Polyoxidonium approved indications. Study population will not be homogenous.

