- Eligible subjects are likely to receive a concomitant treatment with nephrotoxic medicines, including some antibiotics. It may be impossible to estimate precisely the causative agent of observed adverse renal effects.

Regular medical records at study sites (i.e., primary or secondary health care institutions in Slovak Republic) will be used as data source. The potential for missing data for variables of interest in this setting is unknown, and implications for information bias are to be determined.

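### Adjudication of a suspected renal effect allows only case or rejected, with no verdict for insufficient data, although renal data come only from routine practice

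*Protocol*

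**What the plan says.** Primary objective (b) in section 8 is the proportion of subjects who develop adverse renal effects. Section 9.3.2 ties that variable to the definition in section 9.3.1. There, and in the abstract (section 4), the adjudicated conclusion either "will be qualified as event of interest (a case of adverse renal effect) or suspicion about renal toxicity will be rejected". No other outcome is named.

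On how a suspicion arises and what evidence follows:

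- Section 9.3.1 lists laboratory and ECG findings as indicative signs, and also "symptoms of intoxication, e.g. fatigue, nausea, vomiting".
- On suspicion, the investigator is encouraged, not required, "to perform diagnostic workup and collect as much data as possible to confirm or reject the diagnosis of renal impairment". No minimum data set is given.
- Sections 4 and 9.2.5 say that subjects will not "neither undergo any laboratory evaluations, diagnostic or monitoring procedures specifically for the purposes of this study".
- Sections 9.2.4 and 9.3 record laboratory, ECG and other diagnostic results only when they arise in routine practice, and only from the 3 days before enrolment or from the study period. The flow chart marks no laboratory test or ECG at follow-up, only adverse events.

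Section 9.9 adds three statements. What the assessor sees is whatever exists: "A set of available clinical data about the event of interest, presented in a standard format, will be adjudicated by an independent assessor". On misclassification: "A validation is planned which will assess the rate of misclassification and correct the estimates accordingly". On completeness: "The potential for missing data for variables of interest in this setting is unknown".

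**The concern.** A two-way verdict works when every suspected subject arrives with enough data to decide. This protocol does not secure that. A patient treated for an infection may report fatigue or nausea, be suspected of a renal effect, and reach the assessor without a creatinine, urea, potassium or urine protein result. The honest answer is then that the question cannot be settled, and the protocol has no place to record it.

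The assessor must still choose. Nothing in the protocol says which way, so an unwritten habit of the assessor decides part of a primary endpoint. If undecidable suspicions are usually rejected, lack of evidence is tabulated as evidence of no renal effect, and a low or zero proportion looks firmer than it is. That matters because section 9.1 names evidence about the absence of risks among the study's aims, and section 7.2 reports no renal adverse effects so far, so few or no cases are to be expected.

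The later analysis plan cannot repair this. The verdict is itself collected data. If only two values are recorded, a rejection based on normal results can no longer be separated from one made for want of results.

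**Working it through.** The protocol gives no computed figure on this point. Section 9.5 says that 500 subjects was not derived from a sample-size calculation, so there is nothing to reproduce. The check has two steps.

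**1. Does any passage supply what a suspected subject without data would need?**

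| Needed | Where one would look | Found |
|---|---|---|
| A third verdict | 9.3.1, section 4 | No; two outcomes only |
| A minimum data set before adjudication | 9.3.1, 9.9 | No; the available data, in a standard format |
| A default when data are insufficient | 9.3.1, 9.9 | No |
| An evidence threshold for a case | 9.3.1 | No; symptoms stand beside laboratory signs |
| A later correction | 9.9 | Announced, without a method |

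The gap is real. The fourth row also shows that the text does not settle which way such a subject goes.

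**2. How much could it move the result?**

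Inputs: n = 500 (section 9.5); c = adjudicated cases and u = suspected but unassessable subjects. The documents give neither c nor u. Both are assumed here, with u from 1 to 10.

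Exact (Clopper-Pearson) 95% limits for x out of n:

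- lower = 2.5% quantile of Beta(x, n − x + 1), or 0 when x = 0
- upper = 97.5% quantile of Beta(x + 1, n − x)

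For x = 0 the upper limit is 1 − 0.025^(1/500) = 0.74%. Each unassessable subject moves the estimate by 1/500 = 0.2 percentage points, depending on the verdict it is given.

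| c | u | u counted as rejected: c/500 | u counted as cases: (c + u)/500 |
|---|---|---|---|
| 0 | 1 | 0.00% (0.00–0.74) | 0.20% (0.01–1.11) |
| 0 | 3 | 0.00% (0.00–0.74) | 0.60% (0.12–1.74) |
| 0 | 5 | 0.00% (0.00–0.74) | 1.00% (0.33–2.32) |
| 0 | 10 | 0.00% (0.00–0.74) | 2.00% (0.96–3.65) |
| 2 | 5 | 0.40% (0.05–1.44) | 1.40% (0.56–2.86) |

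With no adjudicated case, 3 unassessable subjects separate upper limits of 0.74% and 1.74%, a ratio of 1.74/0.74 = 2.4. Five separate an estimate of zero from one of 1.0%, the lower edge of the common band (1/100) in section 9.5.

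**The case against.** Four arguments stand against the point.

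*The text does not send these subjects to rejected.* A reader might infer that a suspicion without data can only be rejected, and that the renal proportion is therefore biased downwards. The protocol does not support that. Section 9.3.1 sets no evidence threshold and no default, and section 4 describes the event itself as signs or symptoms, so an assessor may call a case on clinical grounds. This objection stands. Under-counting is plausible because a case has to be affirmatively concluded, but it is not built into the rule. What remains is that the choice is unstated.

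*The work-up and the bar on study procedures do not contradict each other.* A reader might infer a flat contradiction between sections 9.3.1 and 9.2.5. The bar covers only procedures done specifically for the study, and a work-up prompted by suspicion in one patient can be ordinary care. Section 9.9 links the two by having investigators gather as much on the event of interest ("adverse renal effects) as possible within the frame of routine practice"). This largely stands: it is a tension. But the linking words are in the limitations section, not in the two sections that tell sites what to do.

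*The protocol already admits the problem.* Section 9.9 acknowledges misclassification and missing data, and announces a validation. Symptoms behind a rejected suspicion also remain on file as adverse events under section 11.2, and count as adverse drug reactions if judged related. That is fair, and such subjects do not vanish. But none of this adds a third category or a method for the renal proportion, and a correction for misclassification would itself benefit from knowing which rejections lacked evidence.

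*Intervals and tables belong in the analysis plan.* That holds for the interval method and table layout. It does not hold for the verdict categories, which are fixed when adjudication takes place.

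**Conclusion.** The point holds as a gap in the outcome definition. Every suspected renal effect must become a case or a rejection, while the protocol makes it foreseeable that some will lack the data for either. Those subjects are liable to be misclassified in the primary renal proportion by a choice nobody has written down.

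The sensitivity to small numbers follows from n = 500 alone. The number of unassessable subjects is pure assumption and could be zero, so the tabulated figures show scale and are not a forecast. Counting all such subjects as cases gives an outer bound, not an estimate. The change should be made before adjudication begins, because the missing category may not be recoverable afterwards.

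**What to change.** In section 9.3.1, and in the matching text of section 4, give the assessor three verdicts:

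1. confirmed adverse renal effect;
2. suspicion rejected on evidence;
3. not assessable for lack of data.

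Report the number of subjects in each. Give the renal proportion twice, each with an exact 95% interval: confirmed/N, with not-assessable subjects counted as non-cases, and (confirmed + not assessable)/N, with them counted as possible cases. The interval method and table layout can go into the analysis plan; the three verdicts must be in the protocol and on the adjudication form.

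Separately, reconcile three statements so that sites read one consistent rule: the encouragement of a work-up (sections 4 and 9.3.1), the bar on study-specific procedures (sections 4 and 9.2.5), and the limit to routine practice (section 9.9). How they are reconciled is for the sponsor to decide.

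The cost is one more category on the form, a few sentences in the protocol and one more row in a table. The third verdict requires no extra assessor and no extra procedure for subjects. The downside is that the headline proportion will stand beside a less favourable upper figure whenever some subjects cannot be assessed.

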9.3.2. Safety variables

Safety variables include:

- proportion of subjects with adverse renal effects (as defined in Section 9.3.1)
- proportion of subjects, who experienced any AE;
- proportion of subjects with ADRs;
- proportion of subjects experiencing serious adverse events (SAEs);
- proportion of subjects with serious ADRs;
- severity of AEs;

- number of subjects who discontinued the study and the reasons for drop-outs;
- global assessment of tolerability by investigators: very good (no intolerance reactions), good (occasional intolerance reactions), moderate (frequent intolerance reactions), poor (intolerance reactions after every use);
- global assessment of tolerability by subjects: very good, good, moderate and poor.

9.3.3. Clinical benefit variables

Clinical benefit assessment includes the following variables:

- global assessment of improvement by subjects score (0 to 4 scale: 0=much worse; 1= somewhat worse; 2=same; 3=somewhat improved; 4 = greatly improved)
- global assessment of improvement by investigators score (0 to 5 scale: 0 = worse; 1 = no appreciable improvement; 2 = slight improvement; 3 = moderate improvement; 4 = marked improvement; 5 = complete resolution)
- mean duration of primary treatment of disease (i.e., days with antibiotic use in case of infection or antiallergic medication in case of allergies),
- days with fever $>38^{\circ}\text{C}$ /days with symptoms,
- total and differential WBC count in blood and urine (if data are available).

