- proportion of subjects with serious ADRs;
- severity of AEs;
- number of subjects who discontinued the study and the reasons for drop-outs;
- global assessment of tolerability by investigators: very good (no intolerance reactions), good (occasional intolerance reactions), moderate (frequent intolerance reactions), poor (intolerance reactions after every use);
- global assessment of tolerability by subjects: very good, good, moderate and poor

Clinical benefit assessment includes the following variables:

- global assessment of improvement by subjects score (0 to 4 scale: 0=much worse; 1= somewhat worse; 2=same; 3=somewhat improved; 4 = greatly improved)
- global assessment of improvement by investigators score (0 to 5 scale: 0 = worse; 1 = no appreciable improvement; 2 = slight improvement; 3 = moderate improvement; 4 = marked improvement; 5 = complete resolution)
- mean duration of primary treatment of disease (i.e., days with antibiotic use in case of infection or antiallergic medication in case of allergies),
- days with fever >38°C/days with symptoms,
- total and differential WBC count in blood and urine (if data are available).

Data sources

Data collection will be based on the review of medical records and routine examination of subjects. Regular medical records at study sites will serve as data sources.

Study size

Approximately 500 adult subjects

Data analysis

Descriptive and comparative statistical methods will be used.

A stratified analysis of main event of interest (i.e., adverse renal effect) will be performed by prior renal impairment and by use of concomitant nephrotoxic medicines to control confounders. Logistic regression will be employed to determine factors as possible predictors of adverse renal effect.

Stratified analysis by indication will be performed to investigate safety profile and clinical benefit in different subgroups of subjects.

Milestones

First eligible subject is planned to enrol on May 2016. Last subject last visit is expected to occur in November 2016.

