8. RESEARCH QUESTION AND OBJECTIVES

This PASS aims to collect data on the safety of Polyoxidonium in patients, for whom Polyoxidonium is prescribed in routine practice in accordance with the terms of the marketing authorisation (MA). This study is a part of a Risk Management Plan (RMP).

The primary objective is:

- (a) to assess the frequency of adverse drug reactions
- (b) to estimate the proportion of subjects, who develop signs and symptoms of adverse renal effects associated with the use of Polyoxidonium.

Secondary objective is to evaluate the clinical benefit of Polyoxidonium by evaluating the following variables:

- (a) overall clinical improvement as assessed by investigators and subjects
- (b) mean duration of primary treatment of disease
- (c) mean number of days with fever $>38^{\circ}\text{C}$ and (or) disease symptoms
- (d) change in total and differential white blood cells (WBC) count (blood and urine) from baseline to the end of treatment (if data are available).

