9.2.1. Subject inclusion criteria

To be eligible for participation in this study, the patient must:

- (a) be male or female at least 18 years of age.
- (b) receive Polyoxidonium prescription in accordance to the SmPC currently approved in Slovakia, i.e., for the treatment of any of the following diseases or conditions accompanied by secondary immunodeficiency:
 - chronic recurrent bacterial infection;
 - chronic recurrent viral infection;
 - acute bacterial infection;
 - acute viral infection;
 - allergic disease (pollinosis, bronchial asthma, atopic dermatitis).
- (c) be informed about the study and provide written consent to participate.

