4.2 Posology and method of administration

Polyoxidonium can be administered in form of either monotherapy or in complex therapy together with antibiotics, antivirals, antimycotics or antihistaminics, broncholytics, corticosteroids, beta-agonists or cytostatics.

Posology

Polyoxidonium is administered to adults depending on the diagnosis and degree of the disease.

Acute inflammatory diseases, complicated forms of allergic disturbances: 6 mg daily for 3 days, then every second day; one cure comprises of 5-10 injections;

Chronic inflammatory diseases: five injections of 6 mg every second day, then twice a week; one cure comprises of 10 injections;

- urogenital diseases: 6 mg every second day, one cure comprises of 10 injections. Concomitant use of chemical drugs is recommended.

- chronic recurrent herpes simplex: 6 mg every second day, one cure comprises of 10 injections, concomitant use of drugs for treatment of herpes is recommended, interferons and interferone inductors.
- allergic disturbances: 6 mg during 2 days, then 6 mg every second day one cure comprises of 5 injections. The drug should be administered concomitantly with the antihistamine and other antiallergic drugs.
- oncological diseases: prior and after chemotherapy 6-12 mg every second day, one cure comprise of at least 10 injections.
- correction of immunodeficiency in patients with decreased cell immunity caused by primary therapy: 6 mg once to twice a week, 2-3 months to 1 year.

Experiences with the use in children are limited.

Method of administration

Dissolve the content of vial (ampoule) in 1.5 – 2 ml water for injections or isotonic saline solution. The solution should be clear, without any mechanical impurities. Do not administer turbid solution.

The drug product should be administered intramuscularly, the slow application for 15-20 second is recommended. Intramuscular injection site should be deltoid muscle of upper limb or outer quadrant of thigh muscle.

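### Duration of primary treatment is defined as antibiotic days for every infection, so it does not measure primary treatment in the two viral indications

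*Protocol*

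**What the plan says.** Section 8 lists, as secondary objective (b), the "mean duration of primary treatment of disease". It names no drug class. Section 9.3.3 then defines the variable: "mean duration of primary treatment of disease (i.e., days with antibiotic use in case of infection or antiallergic medication in case of allergies"). The abstract carries the same rule: "days with antibiotic use in case of infection or antiallergic medication in case of allergies".

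The eligible indications in section 9.2.1 include "chronic recurrent viral infection" and "acute viral infection". Section 9.2.6 gives recurrent herpes simplex its own regimen.

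On accompanying drugs, section 9.2.5 says that "Polyoxidonium may be administered as monotherapy or concomitantly with antibiotics, antivirals, antifungals, and antihistamines", among other classes. For recurrent herpes, section 4.2 of the annexed SmPC (Annex 4) adds that "concomitant use of drugs for treatment of herpes is recommended".

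Section 9.3 has the eCRF record the type of infection, the primary treatment and its duration, and for each drug its identity, start and stop dates and reason for use. Section 9.7.1 plans an analysis of clinical benefit by indication. Section 9.7.3 admits to the benefit analyses subjects who had at least one dose and whose benefit variables are available at the end of study.

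**The concern.** The definition is introduced by *i.e.*, so it is closed: every infection is scored on antibiotic days, and there is no viral branch. Yet the protocol enrols viral infections and itself treats antivirals as a class distinct from antibiotics. Followed as written, the rule scores viral subjects on a drug class that need not be their primary treatment.

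At stake is one of the four components of the clinical benefit objective. Reporting by indication keeps the bacterial and allergic strata clean but leaves the viral strata without a meaningful value. Any mean taken over all infections mixes durations of primary treatment with values that are something else.

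**Working it through.** The protocol states no expected duration, standard deviation or split by indication, so there is no figure to reproduce. The check has two parts.

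**1. The text, set side by side.**

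- Objective (b), section 8: primary treatment, any drug class.
- eCRF item, section 9.3: primary treatment and its duration, with the type of infection, any drug class.
- Variable, section 9.3.3 and abstract: antibiotics for infection, antiallergic drugs for allergy.
- Population, section 9.2.1: four infection indications and one allergic; two of the four are viral.
- Drug classes, section 9.2.5: antibiotics, antivirals and antifungals are separate items, so the word antibiotic cannot be stretched to mean any anti-infective.

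The variable is narrower than both the objective it serves and the data collected for it, and the part left out is the viral indications. A viral subject can yield only three results: zero days, no value, or the length of an antibiotic course taken for another reason. None is the duration of primary treatment of the viral disease.

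**2. What this does to a pooled infection mean (illustration only).** Every input below is an assumption.

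- v = viral share of infection subjects
- q = share of viral subjects who also take an antibiotic
- B = 10, mean antibiotic days in bacterial subjects, all of whom are taken to receive one
- V = 7, mean days of primary treatment in viral subjects; antibiotic courses in viral subjects are also set to 7 days

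Formulas:

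- Rule as written, non-users counted as 0: (1 − v)B + vqV
- Rule as written, non-users treated as not available: [(1 − v)B + vqV] / [(1 − v) + vq]
- Definition matched to the infection: (1 − v)B + vV

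For v = 0.50 and q = 0 these give 0.5 × 10 = 5.0; 5.0 / 0.5 = 10.0; and 5.0 + 0.5 × 7 = 8.5. The full set, with each difference taken from the matched mean:

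| v | q | Non-users = 0 | Non-users left out | Matched | Difference, zero | Difference, left out |
|---|---|---|---|---|---|---|
| 0.10 | 0 | 9.0 | 10.0 | 9.7 | −7% | +3% |
| 0.25 | 0 | 7.5 | 10.0 | 9.25 | −19% | +8% |
| 0.50 | 0 | 5.0 | 10.0 | 8.5 | −41% | +18% |
| 0.75 | 0 | 2.5 | 10.0 | 7.75 | −68% | +29% |
| 0.10 | 0.5 | 9.35 | 9.84 | 9.7 | −4% | +1% |
| 0.25 | 0.5 | 8.375 | 9.57 | 9.25 | −9% | +3% |
| 0.50 | 0.5 | 6.75 | 9.0 | 8.5 | −21% | +6% |
| 0.75 | 0.5 | 5.125 | 8.2 | 7.75 | −34% | +6% |

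With q = 0 and non-users left out, the error is B − [(1 − v)B + vV] = v(B − V), so its sign depends on which group is treated longer. Swapping the assumed durations (B = 7, V = 10, v = 0.50) gives 7.0 against 8.5, which is −18%.

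Within a viral stratum the share v plays no part. With q = 0 the rule gives either a mean of 0 or no observations at all. With q above 0 it describes antibiotic courses.

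**The case against.** The strongest reply is that little harm follows. The variable is secondary and descriptive, in an uncontrolled exploratory study. Objective (b) and the eCRF item are worded generally, so no data are lost. Analysis by indication is already planned, no section commits to a pooled infection mean, and section 9.7 lets the SAP depart from the statistical section if the change is documented. How to count subjects with no primary drug is ordinary SAP detail.

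Most of this stands, and it limits the weight of the point. It does not remove it: the protocol does not leave the definition open but states it twice, and an analysis that follows it carries the error into the viral strata.

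A reader might go further and infer that the rule pulls the mean toward zero and so makes treatment look shorter and more successful. The documents do not support that. The pull toward zero needs non-users to be entered as 0 days. This is a natural reading of a count of antibiotic days, but section 9.7.3 equally allows them to be treated as not available, and the error can then go either way. Some viral subjects may also take antibiotics, which shrinks it. As for apparent benefit, the study has no comparator, and the protocol gives no target or historical duration against which a mean would look short.

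It is also fair to say that the documents name accompanying drugs for only one viral disease, recurrent herpes. They do not establish what primary treatment is in acute viral infection, so the definition should rest on what is recorded as primary treatment.

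**Conclusion.** The point holds as an error in a stated definition. For the two viral indications, the variable in section 9.3.3 and the abstract does not measure what objective (b) names, whatever the viral share and however non-users are counted. The planned viral strata are uninterpretable on this variable.

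Any pooled infection mean is distorted, but by an unknown amount in an unknown direction. Under the durations first assumed above (B = 10, V = 7), the error ranges from −68% to +29% across viral shares of 10% to 75%. Those figures show how far the result depends on inputs the protocol does not give; they do not estimate the error in this study. The correction should be made, but it is modest in weight: the primary objectives, on adverse drug reactions and renal effects, are untouched.

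**What to change.** In section 9.3.3 and in the abstract, define the variable as days on the drug class recorded as primary treatment for the subject's indication: antibacterial drugs for bacterial infection, antiviral drugs for viral infection, antiallergic drugs for allergic disease. Derive it from the data that section 9.3 already collects.

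Report it by indication, and beside each mean show the number of subjects with no primary drug treatment. That count should stay visible and not be dropped silently, because section 9.2.5 allows Polyoxidonium as monotherapy: for such a subject zero days may be a true value, and a mean over treated subjects only answers a different question. The SAP can say which mean is shown, provided the count stands next to it.

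The cost is a wording change in two places and one derivation rule. No new data item or visit is needed. The separate strata will be smaller than a pooled group, so each mean will be less precise.
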